12.1.3 Methods for Evaluation of Disease

All measurements should be taken and recorded in metric notation using a ruler, calipers, or a digital measurement tool. All baseline evaluations should be performed as closely as possible to the beginning of treatment and never more than 4 weeks before the beginning of the treatment.

The same method of assessment and the same technique should be used to characterize each identified and reported lesion at baseline and during follow-up. Imaging-based evaluation is preferred to evaluation by clinical examination unless the lesion(s) being followed cannot be

imaged but are assessable by clinical exam.

Clinical lesions. Clinical lesions will only be considered measurable when they are superficial (*e.g.*, skin nodules and palpable lymph nodes) and ≥ 10 mm in diameter as assessed using calipers (*e.g.*, skin nodules). In the case of skin lesions, documentation by color photography, including a ruler to estimate the size of the lesion, is recommended.

Conventional CT and MRI. This guideline has defined measurability of lesions on CT scan based on the assumption that CT thickness is 5mm or less. If CT scans have slice thickness greater than 5 mm, the minimum size of a measurable lesion should be twice the slice thickness. MRI is also acceptable in certain situations (*e.g.* for body scans).

Use of MRI remains a complex issue. MRI has excellent contrast, spatial, and temporal resolution; however, there are many image acquisition variables involved in MRI, which greatly impact image quality, lesion conspicuity, and measurement. Furthermore, the availability of MRI is variable globally. As with CT, if an MRI is performed, the technical specifications of the scanning sequences used should be optimized for the evaluation of the type and site of disease. Furthermore, as with CT, the modality used at follow-up should be the same as was used at baseline and the lesions should be measured/assessed on the same pulse sequence. It is beyond the scope of the RECIST guidelines to prescribe specific MRI pulse sequence parameters for all scanners, body parts, and diseases. Ideally, the same type of scanner should be used and the image acquisition protocol should be followed as closely as possible to prior scans. Body scans should be performed with breath-hold scanning techniques, if possible.

Ultrasound. Ultrasound is not useful in assessment of lesion size and should not be used as a method of measurement. Ultrasound examinations cannot be reproduced in their entirety for independent review at a later date and, because they are operator dependent, it cannot be guaranteed that the same technique and measurements will be taken from one assessment to the next. If new lesions are identified by ultrasound in the course of the study, confirmation by CT or MRI is advised. If there is concern about radiation exposure from CT, MRI may be used instead of CT in selected instances.

The cytological confirmation of the neoplastic origin of any effusion that appears or worsens during treatment when the measurable tumor has met criteria for response or stable disease is mandatory to differentiate between response or stable disease (an effusion may be a side effect of the treatment) and progressive disease.

12.1.4 Response Criteria

12.1.4.1 Evaluation of Target Lesions

Complete Response (CR): Disappearance of all target lesions. Any pathological lymph nodes (whether target or non-target) must have reduction in short axis to <10 mm.

Partial Response (PR): At least a 30% decrease in the sum of the diameters of target lesions, taking as reference the baseline sum diameters.

Progressive Disease (PD): At least a 20% increase in the sum of the diameters of target lesions, taking as reference the smallest sum on study (this includes the baseline sum if that is the smallest on study). In addition to the relative increase of 20%, the sum must also demonstrate an absolute increase of at least 5 mm. (Note: the appearance of one or more new lesions is also considered progressions).

Stable Disease (SD): Neither sufficient shrinkage to qualify for PR nor sufficient increase to qualify for PD, taking as reference the smallest sum diameters while on study.

12.1.4.2 Evaluation of Non-Target Lesions

Complete Response (CR): Disappearance of all non-target lesions and normalization of tumor marker level. All lymph nodes must be non-pathological in size (<10 mm short axis).

Non-CR/Non-PD: Persistence of one or more non-target lesion(s) and/or maintenance of tumor marker level above the normal limits.

Progressive Disease (PD): Appearance of one or more new lesions and/or *unequivocal progression* of existing non-target lesions. *Unequivocal progression* should not normally trump target lesion status. It must be representative of overall disease status change, not a single lesion increase.

Although a clear progression of “non-target” lesions only is exceptional, the opinion of the treating physician should prevail in such circumstances, and the progression status should be confirmed at a later time by the review panel (or Principal Investigator).

12.1.4.3 Evaluation of New Lesions

The finding of a new lesion should be unequivocal (i.e. not due to difference in scanning technique, imaging modality, or findings thought to represent something other than tumor (for example, some ‘new’ bone lesions may be simply healing or flare of pre-existing lesions). However, a lesion identified on a follow-up scan in an anatomical location that was not scanned at baseline is considered new and will indicate PD. If a new lesion is equivocal (because of small size etc.), follow-up evaluation will clarify if it truly represents new disease and if PD is confirmed, progression should be declared using the date of the initial scan on which the lesion was discovered.

12.1.4.4 Evaluation of Best Overall Response

The best overall response is the best response recorded from the start of the treatment until disease progression/recurrence (taking as reference for progressive disease the smallest measurements recorded since the treatment started). The patient's best response assignment will depend on the achievement of both measurement and confirmation criteria. Evaluation of best overall response should be performed according to **Table 16** and **Table 17** guidelines.

Table 16. Evaluation of best overall response in patients with measurable disease (target disease).

Target Lesions	Non-Target Lesions	New Lesions	Overall Response	Best Overall Response when Confirmation is Required*
CR	CR	No	CR	≥ 4 wks Confirmation**
CR	Non-CR/Non-PD	No	PR	
CR	Not evaluated	No	PR	
PR	Non-CR/Non-PD/not evaluated	No	PR	≥ 4 wks Confirmation**
SD	Non-CR/Non-PD/not evaluated	No	SD	Documented at least once ≥ 4 weeks from baseline**
PD	Any	Yes or No	PD	no prior SD, PR or CR
Any	PD***	Yes or No	PD	
Any	Any	Yes	PD	

* See RECIST 1.1 manuscript for further details on what is evidence of a new lesion.
** Only for non-randomized trials with response as primary endpoint.
*** In exceptional circumstances, unequivocal progression in non-target lesions may be accepted as disease progression.

Note: Participants with a global deterioration of health status requiring discontinuation of treatment without objective evidence of disease progression at that time should be reported as “*symptomatic deterioration*.” Every effort should be made to document the objective progression even after discontinuation of treatment.

Table 17. Evaluation of best overall response in patients with non-measurable disease (non-target disease).

Non-Target Lesions	New Lesions	Overall Response
CR	No	CR
Non-CR/non-PD	No	Non-CR/non-PD*
Not all evaluated	No	not evaluated
Unequivocal PD	Yes or No	PD
Any	Yes	PD

* ‘Non-CR/non-PD’ is preferred over ‘stable disease’ for non-target disease since SD is increasingly used as an endpoint for assessment of efficacy in some trials so to assign this category when no lesions can be measured is not advised

12.1.4.5 Duration of Response

Duration of overall response: The duration of overall response is measured from the time measurement criteria are met for CR or PR (whichever is first recorded) until the first date that recurrent or progressive disease is objectively documented (taking as reference for progressive disease the smallest measurements recorded since the treatment started, or death due to any cause. Participants without events reported are censored at the last disease evaluation).

Duration of overall complete response: The duration of overall CR is measured from the time measurement criteria are first met for CR until the first date that progressive disease is objectively documented, or death due to any cause. Participants without events reported are censored at the last disease evaluation.

Duration of stable disease: Stable disease is measured from the start of the treatment until the criteria for progression are met, taking as reference the smallest measurements recorded since the treatment started, including the baseline measurements.

12.1.5 Response Review

Tumors will be assessed for response and progression by RECIST version 1.1 by central radiology review.

12.1.6 Progression-Free Survival

Overall Survival: Overall Survival (OS) is defined as the time from trial treatment start to death due to any cause, or censored at date last known alive.

Progression-Free Survival: Progression-Free Survival (PFS) is defined as the time from trial treatment start to the earlier of progression or death due to any cause. Participants alive without disease progression are censored at date of last disease evaluation.

Time to Progression: Time to Progression (TTP) is defined as the time from trial treatment start to progression, or censored at date of last disease evaluation for those without progression reported.

13. DATA REPORTING / REGULATORY REQUIREMENTS

Adverse event lists, guidelines, and instructions for AE reporting can be found in Section 7.0 (Adverse Events: List and Reporting Requirements).

13.1 Data Reporting

13.1.1 Method

The Office of Data Quality (ODQ) will collect, manage, and perform quality checks on the data for this study.

13.1.2 Responsibility for Data Submission

Investigative sites within DF/HCC or DF/PCC are responsible for submitting data and/or data forms to the Office of Data Quality (ODQ) in accordance with DF/HCC policies.

13.1.3 Data Safety Monitoring

The DF/HCC Data and Safety Monitoring Committee (DSMC) will review and monitor toxicity and accrual data from this study. The committee is composed of medical oncologists, research nurses, pharmacists and biostatisticians with direct experience in cancer clinical research. Information that raises any questions about participant safety will be addressed with the Overall PI and study team.

The DSMC will review each protocol up to four times a year with the frequency determined by the outcome of previous reviews. Information to be provided to the committee may include: up-to-date participant accrual; current dose level information; DLT information; all grade 2 or higher unexpected adverse events that have been reported; summary of all deaths occurring within 30 days of intervention for Phase I or II protocols; for gene therapy protocols, summary of all deaths while being treated and during active follow-up; any response information; audit results, and a summary provided by the study team. Other information (e.g. scans, laboratory values) will be provided upon request.

13.2 Multi-Center Guidelines

This protocol will adhere to DF/HCC Policy MULTI-100 and the requirements of the DF/HCC Multi-Center Data and Safety Monitoring Plan. The specific responsibilities of the Overall PI, Coordinating Center, and External Sites and the procedures for auditing are presented in Appendix C.

14. STATISTICAL CONSIDERATIONS

This is a multi-center, open-label, phase I/IB study of abemaciclib (arm 1) or abemaciclib plus MK-6482 (arm 2) in patients with advanced refractory ccRCC.

The primary objective of arm 1 is to evaluate the objective response rate of abemaciclib in this population.

The co-primary objectives in arm 2 are to determine the MTD of abemaciclib plus MK-6482, and to determine the objective response rate of abemaciclib plus MK-6482 at the MTD in this population.

Arm 2 will be opened after enrollment of arm 1 is completed.

14.1 Endpoints

14.1.1 Primary Endpoint

Arm 1

Objective response rate (ORR) defined as the percentage of patients with partial (PR) or complete response (CR) as best overall response according to Response Evaluation Criteria in Solid Tumors (RECIST) 1.1 by central review.

Arm 2

MTD of abemaciclib plus MK-6482, defined as the highest dose studied at which no more than 1 of 6 subjects has experienced a DLT in cycle 1.

Objective response rate (ORR) defined as the percentage of patients with partial (PR) or complete response (CR) as best overall response according to Response Evaluation Criteria in Solid Tumors (RECIST) 1.1 by central review.

14.1.2 Secondary endpoints

Duration of response (DOR) as defined in section 12.1.4.5.

Progression-free survival (PFS) defined as the time from trial treatment start to the earlier of progression or death due to any cause. Participants alive without disease progression are censored at date of last disease evaluation.

Overall survival (OS) defined as the time from trial treatment start to death due to any cause, or censored at date last known alive.

Safety and tolerability according to NCI CTCAE v5.0.

Quality of life using FKSI-19 and BFI. The FKSI-19 is a 19 item questionnaire with each item scored on a scale of 0-4 for a total score of 0-76 with higher scores indicating fewer symptoms (Appendix D)²⁹. The BFI is a 9 item questionnaire with each item scored on a scale of 0-10. Scores are categorized as mild (1-3), moderate (4-6), or severe (7-10). A global fatigue score can be found by averaging the score obtained on each test item completed (Appendix E)³⁰.

Pharmacokinetics of abemaciclib and MK-6482.

14.1.3 Exploratory endpoints

Pharmacodynamics of abemaciclib and MK-6482.

Correlates of response and survival: clinical and biological data, study of archival tissue, fresh tumor tissue and blood samples collected before and on therapy.

14.2 Sample Size and Accrual

There is limited data regarding clinical activity of abemaciclib and MK-6482 in ccRCC. Activity of abemaciclib has been described in a phase 1 trial in solid tumors that did not involve ccRCC patients¹⁴. Response rates in advanced refractory breast cancer patients treated with abemaciclib single agent was 19.5%¹⁵.

MK-6482 is has been evaluated in a phase I/II trial involving patients with refractory ccRCC. Preliminary data showed that among 55 patients treated at the MTD, objective response rate was 22%. Toxicities involved mainly anemia, hypoxia and edema. Drug discontinuations due to adverse events were less than 10%.

Therefore, in arm 1, planned sample size is 11 patients, allowing a 0.80 probability to observe 2 or more responses if the true ORR is 25% or higher.

Arm 2 will evaluate two dose levels and follow a standard 3+3 dose escalation scheme. Once the MTD is determined and 6 patients have been treated at the MTD, 14 additional patients will be enrolled for a total of 20 patients treated at the MTD. As ORR is 20-25% for ccRCC patients treated with MK-6482 single-agent, we target an ORR of 50% for the combination of abemaciclib plus MK-6482. With a planned sample size of 20 patients treated at the MTD, there is 94% power to distinguish an ORR of 50% from an ORR of 20% under one-stage design (one-sided alpha=0.09). The combination is considered effective if 7 or more responses are observed out of 20.

The total enrollment will be up to 37 patients (11 in arm 1 and 23~26 patients in arm 2). The accrual is expected to be 3-4 patients per month for a duration of 12 months to complete enrollment.

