1. OBJECTIVES

1.1 Study Design

This a two-arm, non-randomized phase 1/1B trial aiming at assessing the safety and activity of abemaciclib alone (arm 1), and abemaciclib plus MK-6482 (arm 2) in patients with advanced refractory clear-cell renal cell carcinoma (rccrc). Imaging assessments will be performed every 8 weeks during the first six months of the study, then every 12 weeks, in both arms. Patients will undergo mandatory biopsies before therapy and at progression if initial response, in the absence of contra-indication.

In arm 1, abemaciclib monotherapy will be given at the recommended starting dose as monotherapy, until radiographic progression, unacceptable toxicity or withdrawal. A total of 11 patients are expected to be enrolled in arm 1 at a rate of 3 patients per month.

Initially, patients will only be enrolled to arm 1, abemaciclib monotherapy to establish a single arm benchmark activity. Once arm 1 is enrolled with ORR data, we will start enrolling on Arm 2 (combination arm).

Arm 2 will follow a standard dose escalation and dose expansion design (3+3). The dose escalation phase will evaluate the MTD of abemaciclib when administered in combination with MK-6482, using two predefined dose levels. The dose expansion phase will treat patients with abemaciclib at the MTD in combination with MK-6482. Patients will be treated until radiographic progression, unacceptable toxicity or withdrawal. A total of 23-26 patients are expected to be enrolled in arm 2 at a rate of 3 patients per month, including a total of 20 patients treated at the MTD of abemaciclib in combination with MK-6482.

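### Should arm 2 be tested against a response rate above 20%, and should the arm 1 result enter its decision rule?

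*Combined protocol and SAP*

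**What the plan says.** Section 14.2 describes the activity data as limited. For MK-6482 in refractory ccRCC it reports preliminary results: "among 55 patients treated at the MTD, objective response rate was 22" per cent. It widens this to a range and sets the goal for the combination: "As ORR is 20-25% for ccRCC patients treated with MK-6482 single-agent, we target an ORR of 50" per cent. The test is then specified: "there is 94% power to distinguish an ORR of 50% from an ORR of 20" per cent, "under one-stage design (one-sided alpha=0.09". Twenty patients are to be treated at the MTD, and 7 or more responses count as effective.

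Arm 1 (abemaciclib alone) has 11 patients, "allowing a 0.80 probability to observe 2 or more responses if the true ORR is 25% or higher". Section 1.1 gives it the purpose of using "abemaciclib monotherapy to establish a single arm benchmark activity", and adds: "Once arm 1 is enrolled with ORR data, we will start enrolling on Arm 2 (combination arm".

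Section 14.3.2 summarises the ORR in both arms with 80% two-sided exact intervals and plans no comparison between arms. Section 14.4 plans no formal stopping rule on the efficacy endpoints.

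**The concern.** Arm 2 has no concurrent control, so the claim that the combination is effective rests on the null rate and the cut-off that goes with it. The plan cites 22% and a range of 20-25% for MK-6482 alone, and then tests against the bottom of that range without saying why. If the single-agent rate is higher than 20%, a combination that adds nothing passes more often than the stated 0.09 suggests.

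The benchmark raises a second question. Arm 1 is run first and its ORR will be known before arm 2 opens, yet nothing says how that ORR bears on the arm 2 conclusion. Read literally, 7 of 20 (35.0%) would be effective even if arm 1 had produced 4 of 11 (36.4%). A use for arm 1 could then be chosen after its result was seen.

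**Working it through.** **Inputs.** From section 14.2: n = 20, cut-off 7, null 0.20, alternative 0.50; MK-6482 alone 22% of 55, range 20-25%; arm 1 n = 11, sizing rate 0.25; abemaciclib alone in breast cancer 19.5%. From section 2.3.1: MK-6482 at the recommended phase 2 dose in ccRCC, 1 response in 6. From section 14.3.2: 80% exact intervals.

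**Formula.** P(X ≥ r | n, p) = Σ C(n,k) p^k (1−p)^(n−k), summed over k = r to n. Intervals are Clopper-Pearson.

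**The plan's own figures.**
- Alpha: P(X ≥ 7 | 20, 0.20) = 0.0867, stated as 0.09.
- Power: P(X ≥ 7 | 20, 0.50) = 0.9423, stated as 94%.
- Arm 1: P(X ≥ 2 | 11, 0.25) = 0.803, stated as 0.80.

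All three reproduce.

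**Sensitivity to the null, and the main alternatives.** The first three probability columns give the chance of passing when the combination is no better than a single agent at that rate. The last two give it when the combination works.

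| Rule | 20% | 22% | 25% | 40% | 50% |
|---|---|---|---|---|---|
| 7 of 20 (plan) | 0.087 | 0.130 | 0.214 | 0.750 | 0.942 |
| 8 of 20 | 0.032 | 0.054 | 0.102 | 0.584 | 0.868 |
| 8 of 22 | 0.056 | 0.090 | 0.162 | 0.710 | 0.933 |

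Keeping error at or below 0.09 and power at or above 0.94 needs 9 of 25 for a 22% null (error 0.079, power 0.946) and 12 of 32 for a 25% null (0.080, 0.945). That is 5 or 12 more patients than planned.

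**How firm is 22%?** If 22% of 55 means 12 responders (an assumption, since the count is not given), the exact 95% interval is 11.8% to 35.0%. A rate of 20% sits well inside it. The other single-agent figures the plan cites are lower: 1/6 = 17% and 19.5%.

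**Reported interval at the cut-off.** For 7 of 20 the 80% interval is 20.7% to 51.8%. It excludes 20% and contains 22% and 25%. For 8 of 22 it is 22.5% to 52.3%, which excludes 22% and still contains 25%.

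**Arm 1 as a comparator.** The chance of 4 or more responses in 11 is 0.287, 0.161, 0.069 and 0.019 at true rates of 25%, 20%, 15% and 10%. The chance that arm 2 passes while its observed ORR is no higher than arm 1's is 0.043 if both true rates are 25%. With the combination at 22% it is 0.028, 0.006 and 0.0016 for abemaciclib alone at 25%, 15% and 10%. At 4 of 11 the 80% interval for arm 1 runs from 16.9% to 59.9%.

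**The case for a change.** The best case for a change is that the question of interest is whether the combination beats a single agent, and the only sizeable ccRCC estimate in the plan is 22%, not 20%. Against that rate the rule errs 13% of the time, and at the top of the plan's own range 21%, while the reader is told only 0.09. Two more patients, less than a month at the stated 3-4 per month, would bring the error at 22% back to about 0.09. A sentence on arm 1 would cost nothing.

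The arithmetic stands, and so does the observation that no reason is given for 20%. The case for changing the design does not:
- The 8 of 22 rule meets 0.09 only after rounding (0.0902). It lowers the pass probability from 0.942 to 0.933 at a true 50% and from 0.750 to 0.710 at 40%.
- It leaves 0.16 at 25%, so the question of why not 25% comes back unchanged.
- The 25% used for arm 1 is a hypothetical sizing rate. Section 14.2 notes that the abemaciclib phase 1 trial had no ccRCC patients, so it is not an observed comparator.
- Under section 5.1, arm 1 starts abemaciclib at 200 mg bid and arm 2 at 100 or 150 mg bid. Arm 1 is therefore not a like-for-like component of the combination.

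The softer requests, to justify 20%, to tabulate the error at 20%, 22% and 25%, and to call arm 1 descriptive, would make the section clearer. They would not alter the cut-off or any reported result.

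**Conclusion.** The concern does not call for a change. The null is stated openly, falls within the plan's 20-25% range, and cannot be told apart from a preliminary 22% in 55 patients. The published alpha and power are correct for it. The cost of choosing 20% is a rise in false-positive probability from 0.087 to 0.130 at 22%, or to 0.214 at 25%. In an early-phase screen with one-sided alpha of 0.09, 80% intervals and a target of 50%, that is a fair trade against more patients or less power. Statisticians could reasonably settle on 20%, 22% or 25%.

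On the benchmark, sections 1.1, 14 and 14.3.2 together describe a non-randomised study in which each arm has its own ORR objective and is summarised separately. An analyst would report the arm 1 ORR alongside arm 2 and leave the 7 of 20 rule alone. The case of a pass with no advantage over arm 1 has a probability of about 4 in 100 if both true rates are 25%, and well under 1 in 100 if abemaciclib alone is at 15% or less and the combination at 22%.

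This rests on exact binomial calculations with all 20 patients counted, and on reading 22% of 55 as 12 responders for the interval only. The reported 80% interval lets any reader set the result against 22% or 25%.
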